## **4. Study Procedures/Overview of Study Design**

### **4.1. Overview of Study Design**

This study is an open-label pilot study to determine the feasibility of DBS of the thalamus (Ce-Spv-Voi complex) in 10 subjects with treatment-resistant Tourette Syndrome (TS). After subjects are determined to have decision-making capacity by an independent psychiatrist or neurologist who is not a member of the study team, they will come in for 3 consecutive baseline visits and will be evaluated by two different study physicians (psychiatrist and/or neurologist) to determine that he/she has a diagnosis of TS. TS symptom scales will be performed at each visit. Subjects who are eligible will undergo a pre-operative diagnostic MRI along with a planning stereotactic planning MRI, and will undergo neurosurgical implantation of the DBS device followed by implantation of a neurostimulator under the chest wall. Subjects will be monitored at Weeks 1, 2, 3, 4 and then at Months 3, 6, 9 and 12 after implantation of the neurostimulator. At each visit, subjects will be assessed for adverse events and will undergo routine procedures for monitoring patients who undergo DBS, including recording concomitant medications, optimization of stimulation parameters, TS symptom scale assessments to document changes in symptoms, and neuropsychological assessment to document any changes in cognition. No blinding will be performed. Subjects will continue their pre-surgical psychiatric medications and any changes in medications will be documented at each study visit.

The subjects will be followed for one year after implantation. We estimate three implantations per year will be performed, implying just over three years required to complete the implantations. We estimate the full

Date: 2/24/2021

Principal Investigator: [name], PhD

Application Number: NA\_00073086

study duration to be 5-6 years to complete the initial 13 Visits for all of the subjects, prior to the long-term follow-up segment of the study which involves visits approximately semiannually for 2 years followed by annually for the duration of device implantation.

Because this study is being conducted on a vulnerable clinical population, an independent psychiatrist that is not a member of the investigational study team with experience in capacity assessments will assess the decision-making capacity of each potential subject prior to any study-related activities.

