## 5. Inclusion/Exclusion Criteria

### 5.1. Study Population

The study group will consist of 10 patients with treatment-resistant Tourette Syndrome to undergo DBS of the thalamic Ce-Spv-Voi complex

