## **6. Drugs/ Substances/ Devices**

Deep Brain Stimulation Therapy (DBS) delivers electrical stimulation to areas in the brain and has been approved to help control symptoms of various movement disorders (e.g. DBS of the subthalamic nucleus in

Date: 2/24/2021

Principal Investigator: [name], PhD

Application Number: NA\_00073086

Parkinson's disease or DBS of the thalamus in essential tremor). The surgery for PD or essential tremor patients places electrodes (plastic and metal tubes of diameter 1/16-1/32 inch) in the subthalamic nucleus or ventral intermediate nucleus of the thalamus as identified by radiologic and physiologic criteria. Once the electrodes are implanted, they will be connected to an implanted stimulator plus pulse generator (IPG). The implantable pulse generator powers the electrode. The DBS electrodes, and stimulator pulse generator (one device) are called the System. DBS is not approved for use in Tourette Syndrome. However, the use of DBS has expanded to psychiatric diseases such as treatment-resistant depression and obsessive-compulsive disorder and is currently in early phase studies in other psychiatric disorders.

The primary implantable pulse generators used in this study are derived from the Medtronic Activa deep brain stimulation system, including the PC and RC 2-channel pulse generator models. As of April 1st, 2021, Medtronic will no longer provide the Activa PC for new or replacement implantations, but will support the Percept model implantable pulse generator. New implantations for this protocol in Tourette Syndrome will also only utilize the Percept model pulse generator.

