## **7. Study Statistics**

### **7.1. Primary Outcome Variable – Efficacy**

The primary outcome variable will be the clinical response of tic symptoms to treatment, as defined by a 40% decrease from baseline in the Yale Global Tic Severity Scale. The cutoff of 40% was chosen to be consistent with the lower end of improvements observed in previous drug trials treating TS when compared to placebo (1). An improvement in at least one of the three participants is a potential indicator that DBS implantation in treatment refractory Tourette Syndrome can be pursued further.

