### **7.4. Statistical Plan**

This is a pilot study looking at using DBS in 10 Tourette Syndrome patients.

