### **7.5. Early Stopping Rules**

Date: 2/24/2021

Principal Investigator: [name], PhD

Application Number: NA\_00073086

DBS will be discontinued if the subject experiences a worsening of his tic or other Tourette symptoms (or OCD, ADHD, depression, or anxiety symptoms) without returning to baseline (prior to DBS implantation) within 4 weeks from the worsening of the symptoms. DBS will be discontinued if subjects experience suicidal ideation or mania that does not improve with turning off the stimulator. DBS will also be discontinued if neurologic symptoms including muscle contractions, flashing lights, electric jolting sensations, increase in dyskinesias will not improve with stimulator setting change and they are severe enough to interfere with patient daily functioning. Finally DBS will be discontinued if subjects are unable to tolerate the stimulator for any reason not foreseen by the investigator and that clearly interferes with subject's functioning.

Subjects will also be removed from the study for any significant adverse events that jeopardize patient safety. This includes any events related to the surgical procedure or subsequent DBS stimulation therapy. The entire study of 10 subjects will be stopped should the number of subjects meeting the above **Early Stopping Rules** reaches 3 at any point in the study. If this occurs before the full subject recruitment goal has been met, no further subjects will be recruited.

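### Section 7.1 ties the plan's only go-forward efficacy signal to three participants, but the trial has 10 and defines no group of three

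*Combined protocol and SAP*

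**What the plan says.** Section 7.1 defines the primary outcome as a 40% fall from baseline in the Yale Global Tic Severity Scale (YGTSS). It then adds one sentence on what result would be encouraging: "An improvement in at least one of the three participants is a potential indicator that DBS implantation" in refractory disease is worth taking further.

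The trial size is 10 everywhere it is stated:

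- Section 5.1: "The study group will consist of 10 patients with treatment-resistant Tourette Syndrome".
- Section 7.4, whose whole content is: "This is a pilot study looking at using DBS in 10 Tourette Syndrome patients".
- Section 7.5: "The entire study of 10 subjects will be stopped should the number of subjects meeting the above".
- The abstract, the objectives in 2.1 and 2.2, and the overview in 4.1 also give 10.

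Section 7.2 defines a 20% response for the secondary scales but attaches no required count. No other section gives an efficacy criterion for going further.

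**The concern.** The sentence refers to a group of three participants as if it had already been introduced, and it has not. A reader cannot tell whether the signal belongs to the first three subjects, to all 10 with a misprinted number, or to a proportion of one in three. Efficacy is a primary objective, and this is the only place where the plan says what efficacy result would justify pursuing an implanted brain device further. If the denominator is left open, it can be settled after the results are known, and the same data could then be called a signal or not. The sentence also does not say whether an improvement means the 40% response defined just before it.

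**Working it through.** **Is there a group of three anywhere?** The other uses of three in the protocol are these:

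| Place | What the three is | An efficacy group? |
|---|---|---|
| 4.1 | Accrual: "We estimate three implantations per year will be performed, implying just over three years required to complete the implantations" | No |
| 4.1, 4.3 to 4.5 | Three baseline visits per subject | No |
| 5.2 | Three medication regimens | No |
| 7.5 | Three subjects meeting the stopping rules halts the study | No, a count out of 10 |

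None of these identifies three participants for an efficacy assessment.

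**Inputs for the arithmetic.** The number 3 is from 7.1 and the number 10 is from 5.1, 7.4 and 7.5. The plan states no alpha, power, null rate or target rate, so it has no figure to reproduce. The true response rate p is an assumption, shown over a range. I also assume that an improvement means the 40% response, that subjects respond independently with the same p, and that all are evaluable.

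**Chance of a signal under each reading.** P(at least 1 of n) = 1 − (1 − p)^n. At p = 10%: 1 − 0.9^3 = 0.271 and 1 − 0.9^10 = 0.651.

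**Chance that the readings disagree.** One responder among the first three is also one among ten, so they differ only when the first three all fail and at least one of the other seven responds: (1 − p)^3 − (1 − p)^10. At p = 10%: 0.729 − 0.349 = 0.380.

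| Assumed p | At least 1 of 3 | At least 1 of 10 | Disagree |
|---|---|---|---|
| 5% | 14% | 40% | 26% |
| 10% | 27% | 65% | 38% |
| 20% | 49% | 89% | 40% |
| 30% | 66% | 97% | 31% |
| 40% | 78% | 99% | 21% |
| 60% | 94% | over 99% | 6% |

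The maximum is where (1 − p)^7 = 3/10, that is p = 0.158, and it equals 0.418.

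**Smallest observed rate that qualifies.** 1/3 = 33%; 1/10 = 10%. To keep the observed rate at one third or more with 10 subjects, the count must be 4, because 3/10 = 30% falls short.

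**What each required count k out of 10 would do.** The table gives P(at least k of 10) and the exact (Clopper-Pearson) 95% interval for k/10.

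| k | p = 10% | p = 20% | p = 40% | 95% interval for k/10 |
|---|---|---|---|---|
| 1 | 65% | 89% | 99% | 0.3% to 44.5% |
| 2 | 26% | 62% | 95% | 2.5% to 55.6% |
| 3 | 7% | 32% | 83% | 6.7% to 65.2% |
| 4 | 1% | 12% | 62% | 12.2% to 73.8% |

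For comparison, 1 of 3 has an exact 95% interval of 0.8% to 90.6%, so the literal reading is the less precise one.

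**The case against.** The best defence is that this is a soft remark in an open-label pilot. The sentence speaks only of a potential indicator, and no enrolment step, analysis or stopping decision depends on it. Pass and fail are labels that a reviewer puts on it. That is fair, and it is why the point does not call for a formal test. But even a loose criterion needs a denominator, and no other text supplies one.

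Second, the 42% figure is a worst case near p = 16%, a rate that no section supports. The background in 3.2 cites a five-patient series with a similar thalamic target in which 3 of 5 improved markedly. At p = 60% the readings disagree only 6% of the time. This stands as a caution about size, although marked improvement in that series is not defined as a 40% YGTSS fall. At such rates at least one of ten is nearly certain, so that reading would screen out very little.

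Third, the number may simply be left over from a smaller design. The documents do not say so, and its origin would not tell a reader which rule applies now.

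Fourth, setting a new count changes more than a misprint. That is correct, and the cost of doing so is set out with the fix.

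**Conclusion.** The concern holds. The efficacy signal in 7.1 does not fit a 10-subject trial, and nothing in the documents resolves the mismatch. In most outcomes the two main readings agree. They disagree with a probability that depends on the unknown response rate: from 6% to 40% at the rates tabulated, with a maximum of 42%. Reading the sentence as one of ten makes it lenient, since a true rate of 10% would give a signal 65% of the time. These figures rest on assumed response rates, independent subjects, and improvement meaning the 40% response. The text should be fixed, but the defect does not invalidate the trial, because the sentence is not a formal decision rule.

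**What to change.** Rewrite the last sentence of 7.1 for the implanted subjects (planned 10). Possible wording: *A responder has a YGTSS score at least 40% lower at [one named visit] than at [one named baseline]. The number of responders out of all implanted subjects will be reported with an exact 95% confidence interval. At least [k] responders out of 10 will be taken as a possible indication that further study is warranted.* Naming the baseline and the visit goes beyond the denominator problem, but a responder cannot be counted without them.

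The sponsor chooses k and prints its pass probabilities from the table beside it. Keeping k = 1 is acceptable if done knowingly. The plan should also say whether k still applies if the rule in 7.5 ends the study early. As an illustration, with 8 implanted, k = 2 is met 19%, 50% and 89% of the time at true rates of 10%, 20% and 40%.

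Record the date on which k was set and which YGTSS results were then known. Section 4.1 states "No blinding will be performed", and section 6 covers replacement implants and says "New implantations for this protocol in Tourette Syndrome will also only utilize the Percept model pulse generator". This suggests that the study may be under way, although the documents give no count. If results were already known, label k as set after sight of the data and make the count with its interval the main report.

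**Cost.** A text amendment to the primary outcome section, with no extra patients, visits or data. It is still a substantive choice. At a true rate of 40%, k = 2 misses 5% of the time (100% − 95%), k = 3 misses 17% and k = 4 misses 38%. Keeping k = 1 nearly avoids such misses, at the price of a weak signal. A k chosen after results are known cannot be presented as prespecified.

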### **3.2 Initial Stimulation Data**

Early clinical reports on the effectiveness of DBS for TS included those of the Dutch Flemish Tourette Surgery Study Group (2, 5) with bilateral thalamic stimulation, as well as a case of bilateral GPi stimulation for refractory TS by Diederich et al. (3). In these two reports, there were substantial reductions in the numbers and frequencies of tics and compulsive behavior (2, 3). Additionally, Flaherty et al. recently published a case of a patient with TS undergoing bilateral anterior internal capsule DBS placement (with the last electrode in the nucleus accumbens.) At 18 months of follow-up the patient demonstrated significant reductions in tic frequency and severity as well (4). A series of 5 patients with TS were examined in a double-blind fashion by Maciunas et al. after undergoing bilateral DBS placement at the Visser-Vandewalle target in the medial and ventral thalamus (31). Four stimulation states were examined in a blinded fashion, including either unilateral stimulation, both on, or no stimulation. The bilateral stimulation state showed statistical improvements in motor and vocal tic numbers and other TS symptom inventories, with 3/5 patients exhibiting marked improvement (31). Additionally, Servello et al. reported on 18 patients undergoing bilateral thalamic stimulation in the same target for refractory TS. These patients demonstrated significant improvements as well up to 18 months of follow-up (32). And more recent positive results were obtained by Ackermans et al. using the thalamic Ce-Spv-Voi complex target in a small double-blind trial involving six patients (6). This group demonstrated a 37% improvement in the Yale Global Tic Severity Scale between DBS on and off states.

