4. A mandatory trial of behavioral interventions in an attempt to reduce the severity of the tics or comorbid symptoms must also be completed by the subject before offering participation in this trial. This may include habit reversal therapies, stress reduction therapies, or other behavioral therapies under investigation for tic suppression (36,37).
5. Subject has both significant vocal and motor tics with a tic subscale score of at least 35 on the YGTSS (Yale Global Tic Severity Scale) at all three Baseline Visits prior to undergoing surgery (20). For subjects with predominantly vocal tics (and minimal motor) causing significant problems this score requirement will be reduced to 18, similarly for subjects with predominantly motor tics (and minimal vocal) causing significant problems the required score will be 18 (38). A portion of the study team, including the surgeon and two neurologists, will determine by consensus which category the subject falls into and whether the tics are a significant problem.
6. All other aspects of the subject's care must be optimized during the preceding 6 months before admission to the study. This includes treatment for comorbid medical, neurological, and psychiatric disorders. Additionally, it includes psychological interventions for any ongoing psychosocial problems the subject may have during the preceding 6 months before study admission.
7. Subject must be ambulatory.
8. Females who are postmenopausal, physically incapable of childbearing, or practicing an acceptable method of birth control. Acceptable methods of birth control include surgical sterilization, hormonal contraceptives, or double-barrier methods (condom or diaphragm with a spermicidal agent or intrauterine device [IUD]). If practicing an acceptable method of birth control, a negative urine pregnancy test result has been obtained at baseline Visits 1 and 3.
9. Subject is determined by an independent psychiatrist with expertise in capacity assessments to have decision-making capacity to provide informed consent.
10. Subject is able to read English, understand and cooperate with study procedures, and has signed a written informed consent form prior to any study procedures.

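### The one-responder signal in Section 7.1 says little about benefit, and no interval is planned for the responder proportion

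*Combined protocol and SAP*

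**What the plan says.** Section 2.1 makes efficacy on tics a primary objective, in 10 subjects. Section 7.1 sets the primary outcome as clinical response, "as defined by a 40% decrease from baseline in the Yale Global Tic Severity Scale". It then gives the only efficacy signal in the plan: "An improvement in at least one of the three participants". Such a result, according to the same section, "is a potential indicator that DBS implantation in treatment refractory Tourette Syndrome can be pursued further".

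The count of three conflicts with the 10 subjects in Sections 2.1, 4.1, 5.1, 7.4 and 7.5. Section 7.4 is a single sentence: "This is a pilot study looking at using DBS in 10 Tourette Syndrome patients". Sections 7.1 to 7.4 contain no background or target response rate, no error rate and no confidence interval. Section 7.2 adds mean changes and a 20% response for other scales, and Section 7.3 adds counts and percentages of adverse events.

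On design, Section 4.1 describes an open-label pilot without a comparison group and states: "No blinding will be performed".

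**The concern.** In an uncontrolled before-after study, some subjects may reach a 40% fall for reasons other than stimulation. Several features of the plan leave room for this:

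- Ratings are unblinded, and the same YGTSS scores guide programming (Sections 4.8 to 4.10).
- Medication changes are recorded but not ruled out (Section 4.1).
- Entry requires significant tics "with a tic subscale score of at least 35 on the YGTSS" at all three baseline visits, or 18 where tics are predominantly vocal or motor (Section 5.2). Some regression toward the mean is therefore possible.

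A bar of one responder is the lowest that can be set, and its chance of being met by background response grows with the number of subjects. Correcting the count from three to 10 without touching the bar therefore makes the signal weaker. At stake is whether the trial's only efficacy criterion can inform a decision to take an intracranial implant further.

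**Working it through.** **No figure to reproduce.** The plan states no error rate, power or sample size calculation.

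**Inputs.** The number of subjects is 3 (Section 7.1 as written) or 10 (rest of the protocol). The bar is at least one responder. The background rate p is not stated. The only benchmark in Section 7.1, "consistent with the lower end of improvements observed in previous drug trials treating TS when compared to placebo", supports the 40% cutoff and is not a proportion of patients responding. I therefore assume p from 1% to 20%.

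**Step 1: chance that background response alone meets the signal.** P(at least 1 of n) = 1 − (1 − p)^n. For example, 1 − 0.9^3 = 0.271 and 1 − 0.9^10 = 0.651.

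| Assumed p | 1 of 3 (as written) | 1 of 10 (count corrected, bar kept) |
|---|---|---|
| 1% | 3.0% | 9.6% |
| 2% | 5.9% | 18.3% |
| 5% | 14.3% | 40.1% |
| 10% | 27.1% | 65.1% |
| 20% | 48.8% | 89.3% |

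With 10 subjects, this chance is 10% or less only if p is at most 1 − 0.9^(1/10) = 1.0%. It is 5% or less only if p is at most 1 − 0.95^(1/10) = 0.5%.

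**Step 2: what one responder shows.** The Clopper-Pearson 95% limits for x of n are the 2.5% quantile of Beta(x, n − x + 1) and the 97.5% quantile of Beta(x + 1, n − x). For 1 of 10 the interval is 0.3% to 44.5%; for 1 of 3 it is 0.8% to 90.6%.

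**Step 3: smallest count of 10 whose lower exact 95% limit exceeds a named background.**

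| Background | Count needed | Its lower limit | Lower limit one count below |
|---|---|---|---|
| 5% | 3 of 10 | 6.7% | 2.5% |
| 10% | 4 of 10 | 12.2% | 6.7% |
| 20% | 6 of 10 | 26.2% | 18.7% |

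The criterion has to be fixed in advance, because another one can give another count. At a 20% background, 5 of 10 keeps the upper tail below 5% (P(X ≥ 5) = 3.3%) but fails the lower-limit criterion.

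**Step 4: chance of reaching the stricter bar when benefit is real.** For 4 or more of 10, P(X ≥ 4) is 83%, 62% and 35% at true response rates of 50%, 40% and 30%. These rates are also assumptions. The cited five-patient series in Section 3.2, "with 3/5 patients exhibiting marked improvement", suggests 60%, at which the chance is 94.5%. That series does not use the 40% YGTSS definition, so 60% is only an illustration.

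**The case against.** The strongest reply is that this is a pilot, and the sentence claims only a potential indicator for further work. No test, error rate or efficacy claim is attached to it. That stands: the criticism is that the signal carries little information, not that a stated type I error is wrong. Efficacy is nevertheless a primary objective, and no other efficacy criterion is given.

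A second reply is that background response may be rare in these patients. Section 5.2 requires at least a year of treatment resistance, at least three adequate medication regimens, a behavioural trial and a high score at three baselines, and a 40% fall is a demanding response. This also has force, and it is why the table starts at 1%. It does not establish a low rate, because regression toward the mean and unblinded rating remain.

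A reader might infer from the 5% to 20% rows that the rule has a false-positive rate of 40% to 89%, or that it is met almost regardless of the truth. The documents do not support this. The rates are assumed, the chance is 9.6% at 1% and 18.3% at 2%, and even at 5% the 10-subject rule is not met 60% of the time. Those rows also describe a rule the protocol does not contain, since it says three and nothing shows that one of 10 was intended.

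**Conclusion.** The point holds in a limited form. Section 7.1's only efficacy signal is weak evidence of benefit, and nothing planned shows how imprecise the responder proportion will be. Over assumed background rates of 1% to 20%, background response alone meets it 3% to 49% of the time as written, and 10% to 89% of the time if only the count is corrected. The bar and the count therefore need to be settled together.

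The calculations take subjects as independent and improvement to mean the 40% response. Section 7.1 does not tie its signal explicitly to that response or to an assessment visit, and Section 4.12 schedules YGTSS at eight visits from initial programming (Visits 6 to 13). If any fall, or a fall at any visit, were enough, the chances would be higher.

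A reader might also infer that adding an interval would let the trial separate stimulation benefit from other causes. It would not: the interval reflects sampling error only and says nothing about expectation or regression toward the mean.

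**What to change.** In Sections 7.1 and 7.4, state that the number of 40% YGTSS responders of 10 will be reported with an exact (Clopper-Pearson) 95% interval. Delete the one-responder sentence, so that the interval carries the conclusion.

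If the sponsor prefers to keep a signal, it should name and justify a background rate and use one criterion only: the lower exact 95% limit exceeds that rate. This means 3 of 10 for 5%, 4 of 10 for 10% and 6 of 10 for 20%.

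The cost is a few sentences and no new data or subjects, but the second option needs a source for the background rate that the documents do not supply. The signal also becomes harder to meet: under a bar of 4 of 10, a true response rate of 40% would be missed 38% of the time and a rate of 30% would be missed 65% of the time. That risk of setting aside a useful treatment is a reason to prefer the first option if no rate can be defended.
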